5.13.3 Determination of sample size

The sample size for this trial is based on perceived appropriate enrollment of 10 patients per year for 3 consecutive years. Since this is a single-arm, active-treatment study, no such calculation of statistical power is needed to quantitate the sample size.

5.14 Data quality assurance

The Pulmonary Research Core will be responsible for data management of this trial, including quality checking of the data. Data will be collected and aggregated in REDCap. Investigators and support personnel from the research core will be responsible for entering the needed data into REDCap. In the event of discrepant data, clarification will be performed by the primary investigators.

6 Assessment of safety

Safety assessments will consist of monitoring and recording adverse events (AE) and serious adverse events (SAE) as defined in this section; measurement of protocol-specified hematology and basic chemistry laboratory values, measurement of protocol-specified vital signs, and other non-protocol specific tests that are deemed critical to the safety evaluation of the patient.

Investigators are responsible for reporting any SAE to Amgen as described below. Amgen will be responsible for reporting SAEs to the appropriate regulatory body.

6.1 Possible risks and discomforts

6.1.1 Carfilzomib Risks

Carfilzomib is approved by the U.S. Food and Drug Administration (FDA) to be used only in certain U.S. patients with relapsed and refractory multiple myeloma that have tried and failed other therapies. It has not been approved to be used for any other disease or condition. In this study, carfilzomib is an investigational study drug because it is not approved for use in all patients in the United States, and it is not approved by some regulatory authorities (the agencies that are responsible for approving the use of a medicine in a country such as the European Medicines Agency and Health Canada).

6.1.2 Adverse effect (AE) definition

An AE is any unfavorable and unintended sign, symptom, or disease temporarily associated with the use of an investigational medicinal product or other protocol-imposed intervention, regardless of attribution.

This includes the following:

AEs not previously observed in the patient that emerge during carfilzomib therapy (days 1through 16, and 28, 42, 90), including signs or symptoms associated with AMR that were not present prior to the AE reporting period.

Complications that occur as a result of protocol-mandated interventions.

AEs that occur prior to the assignment of study treatment that are related to a protocol-mandated intervention.

Preexisting conditions judged by the investigators to have worsened in severity or frequency or changed in character during carfilzomib therapy (days 1through 16, and 28, 42, 90).

6.1.3 Serious adverse effect (SAE) definition

Death

Life threatening experience defined as any adverse experience that places the subject, in the view of the Investigator, at immediate risk of death at the time of occurrence; i.e., it does not include a reaction that, had it occurred in a more severe form, might have caused death.

Requires prolongation of the study hospitalization.

Results in persistent or significant disability/incapacity.

Congenital anomaly/birth defect in the offspring of an exposed subject.

Important medical events that may not result in death, be life-threatening, or require hospitalization, may be considered an SAE, when, based upon appropriate medical judgment, it jeopardizes the subject and may require medical or surgical intervention to prevent one of the outcomes listed in this definition.

All AEs that do not meet these criteria should be regarded as non-serious AEs.

The terms serious and severe are not synonymous. Severity refers to the intensity of an AE; thus, severe AEs may not represent serious AEs. SAEs include only the above items that are based on patient or event outcome or action criteria associated with events that pose a threat to the patient's life or vital functions and require reporting to appropriate regulatory agencies as defined in this section.

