4.4.3 Safety outcomes

Safety outcomes of the study include the following:

- 4.4.3.1 Non-lung irreversible end-organ failure (e.g., end-stage renal disease) any time after day 1 attributable to carfilzomib.
- 4.4.3.2 Incidence of adverse effects (AE) requiring dose-modification (see section 5.3.1.2) any time during days 1-16.
- 4.4.3.3 Incidence of any AE at any time after day 1 as graded by the NIH Common Terminology Criteria for Adverse Events (CTCAE) (appendix B) criteria, as follows:
 - Grade 1: Mild; asymptomatic or mild symptoms; clinical or diagnostic observations only; intervention not indicated.
 - Grade 2: Moderate; minimal, local or noninvasive intervention indicated; limiting ageappropriate instrumental ADL (Instrumental ADL refer to preparing meals, shopping for groceries or clothes, using the telephone, managing money, etc.).
 - Grade 3: Severe or medically significant but not immediately life-threatening; hospitalization or prolongation of hospitalization indicated; disabling; limiting self-care ADL (self-care ADL refer to bathing, dressing and undressing, feeding self, using the toilet, taking medications, and not bedridden).
 - Grade 4: Life-threatening consequences; urgent intervention indicated.

Grade 5: Death related to AE.

- 4.4.3.4 Incidence of hypogammaglobulinemia any time after day 1.
- 4.4.3.5 Incidence of culture-proven *de novo* infection any time after day 1.
- 4.4.3.6 Diagnosis of systemic inflammatory response syndrome (SIRS) any time during days 1-16; requiring at least 2 of the following 4 criteria:

Body temperature: < 36 or > 38 degrees Celsius

Tachycardia: > 90 beats per minute

Tachypnea: > 20 breaths per minute

White blood cells: < 4000 or > 12000 cells/mm³

- 4.4.3.7 Patient death at any time after day 1 attributable to carfilzomib.
- A 1:1 retrospective control group including lung transplant recipients from the University of Pittsburgh with Antibody Mediated Rejection will be created to describe differences in the endpoints using the CFZ-based regimen vs. historic standard of care.

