6.2.3 Assessment of severity and causality of adverse events

Investigators will seek information on AEs and SAEs at each patient contact. All AEs and SAEs, whether reported by the patient or noted by authorized study personnel, will be recorded in the patient's medical record and reported on the AE or SAE forms and reportable SAE on the FDA MedWatch form.

For each AE and SAE recorded, the investigators will make an assessment of seriousness and severity based on the CTCAE criteria, and causality to carfilzomib.

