6.3.7 Prolonged hospitalization

Any AE that results in prolonging of the study hospitalization shall be documented on the FDA Medwatch form as an SAE and be subject to all the rules and regulations of reporting as described in this section.

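### Sections 6.1.3 and 6.3.7 count only a longer study stay as serious, so a new admission after discharge is not an SAE on that ground

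*Combined protocol and SAP*

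**What the plan says.** Section 6.1.3 lists what makes an event serious: death, immediate risk of death, a longer study stay, lasting disability, congenital anomaly, and important medical events. The only item that turns on hospital care is "Requires prolongation of the study hospitalization". Section 6.3.7 has the same scope: "Any AE that results in prolonging of the study hospitalization shall be documented on the FDA Medwatch form as an SAE".

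Section 6.1.3 closes the list twice: "All AEs that do not meet these criteria should be regarded as non-serious AEs", and "SAEs include only the above items that are based on patient or event outcome or action criteria". Its important-medical-event item is permissive: "Important medical events that may not result in death, be life-threatening, or require hospitalization, may be considered an SAE".

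Section 6.2.3 offers a second basis. For each recorded event, "the investigators will make an assessment of seriousness and severity based on the CTCAE criteria, and causality to carfilzomib". The grade 3 text in section 4.4.3.3 includes "hospitalization or prolongation of hospitalization indicated". Yet 6.1.3 also states: "The terms serious and severe are not synonymous".

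On recording, section 5.4.1 makes a new or worse physical-examination finding an AE on the condition that it is judged related to study therapy. Section 6.1.2 defines an AE without regard to attribution. Section 6.2.1 requires any AE or SAE in the reporting period to be recorded. Section 6.2.3 has all of them recorded and then assessed for causality.

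**The concern.** A patient who has gone home and is then readmitted has not had the study stay lengthened. Under 6.1.3 and 6.3.7 the admission itself carries no weight, and the closing sentences direct staff to call the event non-serious unless some other item applies.

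Three things in the plan hang on the label:

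- **Ad hoc DSMB review (4.5).** Otherwise the board sees AE reporting once a year.
- **The separate SAE listing and summary (5.13.2).**
- **Follow-up to resolution or stabilization whatever the cause (6.5).** Section 5.8 follows other ongoing AEs only if they are thought related to carfilzomib.

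Section 3.1 expects the trial to establish the safety of the combination, so the SAE count will be one of its main safety results. A count that leaves out readmissions would be too low.

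The 5.4.1 condition raises a smaller, separate problem. In an open-label single-arm study it puts the investigator's view of causality ahead of the decision to count an examination finding as an AE at all.

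**Working it through.** The plan states no figure to reproduce. The check is a comparison of sections, plus one day count.

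**Step 1. Is a new admission a criterion anywhere?** Sections 6.1.3 and 6.3.7 both refer to the study hospitalization only. No section available for review makes an admission after discharge a criterion. The text just before 6.4.1 was not available and could not be checked. The definition in 6.1.3 is complete and closed as it stands, so the finding does not depend on it.

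**Step 2. Does the important-medical-event clause fill the gap?** Not by rule. It says such events may be considered serious, so it leaves the matter to judgement. It also turns on preventing one of the outcomes listed in the definition, and a new admission is not listed. The clause describes events that may fall short of requiring hospitalization, as though that were already a criterion. This is the best evidence that the omission is a slip.

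**Step 3. Does 6.2.3 fill the gap?** It bases seriousness on CTCAE, and grade 3 names hospitalization, so some staff may call a readmission serious on that ground. But 6.1.3 separates serious from severe and limits SAEs to its own list. Two sections therefore give different tests, which adds ambiguity and does not supply the missing criterion.

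**Step 4. How much of the study period is exposed?** Inputs from section 5.4: minimum stay 16 days; follow-up to day 90.

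- One cycle at the minimum stay: 90 − 16 = 74 days; 74 / 90 = 82%.
- Two cycles, assuming that the second stay is also 16 days and falls within day 90: 90 − 32 = 58 days; 58 / 90 = 64%.

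Longer stays reduce both shares. They count days on which an admission could not meet the only hospitalization criterion. They say nothing about how many admissions occur.

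**Step 5. The 5.4.1 condition against section 6.**

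| Section | Is relatedness needed for an AE to be recorded? |
|---|---|
| 5.4.1 (examination findings) | Yes, as naturally read |
| 6.1.2 | No |
| 6.2.1, reporting period | No |
| 6.2.3 | No; causality is assessed after recording |

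The conflict covers examination findings only. Under 5.4.1 the change from baseline is still noted, so only its status as an AE is filtered.

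**The case against.** The strongest reply is that the event is not lost, only its label. This stands. Section 6.2.2 asks every patient at days 28, 42 and 90, in person or by phone, about new or changed health problems since the last contact. Within the reporting period 6.2.1 requires the event to be recorded and reported to the manufacturer, and 5.13.2 lists it by patient and summarizes it by grade. Section 5.4 adds medical-record review up to day 360. The manufacturer may stop the study on AE incidence or severity (5.10), and unanticipated problems go to the IRB (7.4). A reader might infer that readmissions during the study would go unseen; the documents do not support that.

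A reader might also infer that urgent reporting would fail. At a single center with an investigator-sponsor, the 24-hour notice in 6.4.1 is largely internal, and expedited reporting to the manufacturer is limited to related SUSARs. Nor would the label let the DSMB stop the study early, because 4.5 bars termination before 15 patients are enrolled.

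On 5.4.1, it can be said that *if* does not mean *only if*, and that section 6 governs recording. That is a fair reading, and it limits the harm: counts fall only where staff follow 5.4.1 over three other sections. The sentence still invites the filter.

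Two further inferences are not supported. The rates in the 6.1.4 table come from earlier carfilzomib trials and measure no readmission. The limit in 6.2.1 on recording after the day-90 window need not conflict with 4.4.3.3, which counts AEs at any time after day 1, because that phrase can be read as within a study that ends at day 90.

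**Conclusion.** The omission is real and should be corrected. As written, an AE causing a new admission after discharge is not an SAE because of the admission. It becomes one only through another criterion or by discretion. What can be lost is ad hoc DSMB review, a place in the separate SAE summary, and follow-up of events judged unrelated; the SAE count can be too low.

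The number of affected events cannot be determined from the documents. The 82% is exposure time, and it assumes one cycle and discharge at the 16-day minimum. A reader might take it as the share of SAEs missed, which it is not.

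The 5.4.1 conflict is secondary and confined to examination findings. No efficacy endpoint is affected. Confidence is high in the reading of 6.1.3 and 6.3.7. No size can be claimed for the effect.

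**What to change.** 1. In 6.1.3 and 6.3.7, replace the criterion with: *requires inpatient hospitalization or prolongation of existing hospitalization*. State that the planned admission for a study cycle does not itself count.
2. In 6.2.3, say that seriousness follows 6.1.3 and severity follows CTCAE.
3. In 5.4.1, delete the relatedness condition and keep causality as a separately recorded field, as 6.2.3 already provides.
4. In the same edit, reconcile how AMR-related events are handled. Section 6.1.2 counts new AMR signs or symptoms as AEs, 6.3.6 keeps worsening AMR out of AEs and SAEs, and 6.3.4 makes death from AMR progression an SAE. The sponsor should settle which governs, and so how an admission for worsening AMR is classed; this review does not presume the answer.

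The cost is four sentences and one reconciliation. The downside is somewhat more SAE paperwork, more ad hoc DSMB reviews and higher reported counts. Section 5.13 analyzes data only at study conclusion, so one rule can still govern the final SAE summary for all patients.

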6.1.4 All previously reported AEs related to carfilzomib from clinical trials

Organ system	All adverse reactions, frequency (%)	Grade 3 and above adverse reactions, frequency (%)	Serious adverse reactions, frequency (%)				
Blood and lymphatic sy	Blood and lymphatic system disorders						
Anemia	45.9	22.5	1.9				
Thrombocytopenia	34.9	23.2	1.6				
Neutropenia	23.8	15.7	0.6				
Lymphopenia	12.5	9.9	-				
Leukopenia	10.2	4.3	0.1				
Febrile neutropenia	2.2	1.8	1.6				
Cardiac disorders							
Cardiac failure	4.4	2.9	2.8				
Myocardial infarction	0.8	0.6	0.6				
Cardiac arrest	0.6	0.6	0.6				
Myocardial ischemia	0.4	0.3	0.3				
Eye disorders							
Vision blurred	5.1	< 0.1	-				
Cataract	2.6	1	0.1				
Gastrointestinal disord	ers						
Diarrhea	33.7	2.3	0.8				
Nausea	31.9	0.9	0.1				
Constipation	18.5	0.2	-				
Vomiting	17.1	0.6	0.2				
Abdominal pain	10.6	1.2	0.6				
Dyspepsia	5.8	0.1	-				
Toothache	2.5	0.1	-				
General disorders and a	administration site condi	tions					
Fatigue	43.6	5.9	< 0.1				
Pyrexia	28.2	1.6	2.9				
Edema	21.8	0.6	< 0.1				
Asthenia	12	1.6	0.3				
Chills	10.6	0.1	0.1				
Pain	7	1.3	0.6				
Multiorgan failure	0.5	0.5	0.4				
Infusion site reactions	0.2	-	-				
Hepatobiliary disorders							
Hepatic failure	0.1	< 0.1	< 0.1				
Infections and infestati		T					
Respiratory tract	26.2	3.1	2				
infection							
Pneumonia	12.5	9.3	9.7				
Nasopharyngitis	9.9	< 0.1	< 0.1				
Bronchitis	7.3	1	1.1				
Urinary tract infection	7	1.3	0.9				

Influenza	3.7	0.3	0.4
Sepsis	1.8	1.7	1.5
Viral infection	1.7		< 0.1
	1.7	-	< 0.1
Investigations Increased blood	15.6	2.2	0.5
creatinine	15.6	2.3	0.5
Decreased creatinine	1.0	0.2	
clearance	1.8	0.2	-
	2.4	1 1	
BUN increased	3.4	1.1	-
AST increased	6.8	2	0.1
ALT increased	6	2.4	0.1
C-reactive protein	1.3	0.3	-
Metabolism and nutriti	 		
Hypokalemia	15.8	4.7	0.3
Decreased appetite	15.1	0.3	-
Hyperglycemia	13.3	4.3	0.3
Hypomagnesemia	10.2	0.6	-
Hypocalcemia	9.7	2.4	0.2
Hypophosphatemia	9.4	5.6	< 0.1
Hyponatremia	7.7	4.3	0.3
Hypercalcemia	7.3	2.7	1.9
Hyperuricemia	5.9	1.5	-
Hyperkalemia	5.1	1.4	0.2
Hypoalbuminemia	5.1	2	< 0.1
Dehydration	4	1	0.7
Tumor lysis syndrome	0.7	0.6	0.6
Musculoskeletal and co	nnective tissue disorder	s	
Back pain	19	2.8	0.8
Muscle spasms	15.9	0.5	-
Arthralgia	14.5	1	0.1
Pain in extremity	12.8	1	0.2
Musculoskeletal pain	9.8	1.5	0.1
Musculoskeletal chest	8.8	0.4	0.1
pain			
Muscular weakness	6.2	1.1	0.3
Myalgia	5.7	0.3	-
Nervous system disorde	ers		
Headache	20.4	1.1	0.3
Dizziness	11.6	0.6	< 0.1
Neuropathy	8.7	1	< 0.1
Parestheisa	8.3	0.2	< 0.1
Hypoesthesia	6.9	0.1	-
Psychiatric disorders			
Insomnia	16.1	0.7	-
Anxiety	6.6	0.3	-
Renal and urinary disor	ders		

			T
Acute kidney injury	5.9	4.5	4.4
Renal failure	3.4	1.6	0.9
Renal impairment	1.6	0.6	0.3
Respiratory, thoracic ar	nd mediastinal disorders		
Dyspnea	27.6	4	2.1
Cough	24.2	0.3	0.1
Epistaxis	7.9	0.4	0.2
Oropharyngeal pain	7.8	-	-
Dysphonia	2.6	-	-
Pulmonary edema	1.6	1	0.9
Pulmonary embolism	1.5	1.3	1.3
Skin and subcutaneous	tissue disorders		
Rash	8	0.5	0.3
Pruritis	5.9	< 0.1	-
Erythema	4.5	-	-
Hyperhidrosis	3.9	-	-
Vascular disorders			
Hypertension	14.9	4.4	0.6
Hypotension	5.6	1.5	0.9
Deep venous	3.1	1.2	1.1
thrombosis			

6.2 Methods and timing for capturing and assessing safety parameters

The investigators are responsible for ensuring that all AEs will be recorded on the AE form and SAEs are recorded on the SAE form. All reportable SAE will be reported on the FDA MedWatch forms and reported to Amgen as defined in this section.

6.2.1 Adverse event reporting period

After informed consent is obtained but before any administration of study drug, only SAEs due to protocol mandated interventions will be recorded. Any AE or SAE at any time after the first infusion of carfilzomib is initiated until day 16, and on days 28, 42, 90 ±14 days must be recorded by the investigators and reported to Amgen as defined in this section. After this period, only SAEs deemed to be related to study drug will be recorded and reported.

Serious Adverse Event Reporting Contact Information:

Amgen Global Safety

Toll-free #:[name]

For countries where the U.S. toll-free # cannot be used: [contact]

Email (Only for sponsors with a secure email connection with Amgen):

[contact]

6.2.2 Eliciting adverse events

A consistent methodology of non-directive questioning for eliciting AEs at all patient evaluation time points will be adopted.

This will include the following two questions directed to study subjects:

How have you felt since your last infusion of carfilzomib?

Have you had any new or changed health problems since you were last seen?

These questions will be asked in person at days 28, 42 and 90 ±14 days, or by phone if patient does not return to their standard of care visit at these time points.

6.2.3 Assessment of severity and causality of adverse events

Investigators will seek information on AEs and SAEs at each patient contact. All AEs and SAEs, whether reported by the patient or noted by authorized study personnel, will be recorded in the patient's medical record and reported on the AE or SAE forms and reportable SAE on the FDA MedWatch form.

For each AE and SAE recorded, the investigators will make an assessment of seriousness and severity based on the CTCAE criteria, and causality to carfilzomib.

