- 2: To test the hypothesis in a prospective interventional clinical trial that addition of carfilzomib to conventional therapy will result in improved or stabilized allograft function. In this trial, lung transplant recipients will be treated with the carfilzomib-based combination protocol and screened with pulmonary function testing to identify whether forced expiratory volume in 1 second returns to pre-AMR diagnosis level.
- 3: To test the hypothesis that lung transplant recipients with AMR have effector B cell/plasma cell populations that can be identified and characterized, and that carfilzomib alters these immune mechanisms. In this trial, we will determine the immunologic phenotype

of these patients and describe functional immune system changes in memory and effector cells, plasma cells, and respective pathologic and immunohistochemical correlates relevant to AMR.

The PICARD-Lung investigators and the study center are highly experienced clinical and translational investigations in lung transplantation. Successful completion of these specific aims will establish the safety and efficacy of combination therapy with carfilzomib/PLEx/IVIG for AMR after lung transplantation and elucidate important clinical and immunologic phenotypes and mechanisms associated with these outcomes. Thus, the results of this trial will advance treatment efforts for AMR, which are desperately needed, as well as provide important insights into the link between AMR and BOS, the latter of which significantly limits long-term outcomes in lung transplant recipients. Lastly, we fully anticipate this study will lay the foundation for future clinical and basic investigation, perhaps at the multi-center level, to further delineate the role and immune effects of carfilzomib in the treatment of AMR and the prevention of BOS.

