4.4.2 Secondary endpoints

Secondary endpoints of this study include the following:

- 4.4.2.1 Absolute change in DSA strength, titer, and complement fixation from day 1 to day 90 and from day 42 to day 90. DSA strength will be determined by Luminex single-antigen bead testing in the neat serum and quantitated in units of mean fluorescent intensity. DSA titer will be determined by Luminex single-antigen bead testing in the diluted serum to 1:16 and quantitated in units of mean fluorescent intensity. DSA complement fixation will be determined by C1q-based Luminex single-antigen bead testing in the neat serum and quantitated in units of mean fluorescent intensity.
- 4.4.2.2 Absolute change in forced expiratory volume in 1 second (FEV1) from day 1 to day 42 and to day 90. FEV1 will be quantitated via UPMC PFT lab standard methods on routine pulmonary function testing obtained in the routine clinical care of these patients.
- 4.4.2.3 Presence or absence of pathologic changes consistent with AMR on transbronchial biopsy from day 1 to day 42. Pathologic changes consistent with AMR will be defined as follows: Complement-4d fixation on >50% (diffuse) of the capillaries in the biopsy by standard immunoperoxidase method, capillaritis by standard hematoxylin and eosin (H&E) stain; or endothelialitis by standard H&E stain.
- 4.4.2.4 Patient death at any time after day 1 attributable to AMR.
- A 1:1 retrospective control group including lung transplant recipients from the University of Pittsburgh with Antibody Mediated Rejection will be created to describe differences in the endpoints using the CFZ-based regimen vs. historic standard of care.

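### The organ-failure and death safety outcomes count only events attributed to carfilzomib, so they understate the combined regimen and cannot be compared with the retrospective controls

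*Combined protocol and SAP*

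**What the plan says.** Section 6.2.3 asks the investigators to judge, for every recorded AE and SAE, seriousness and "severity based on the CTCAE criteria, and causality to carfilzomib". It names no other agent or procedure.

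Two safety outcomes in section 4.4.3 depend on that judgement:

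- 4.4.3.1: "Non-lung irreversible end-organ failure (e.g., end-stage renal disease) any time after day 1 attributable to carfilzomib"
- 4.4.3.7: "Patient death at any time after day 1 attributable to carfilzomib"

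The only other named death endpoint is secondary endpoint 4.4.2.4: "Patient death at any time after day 1 attributable to AMR".

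Section 3.1 states that completing the aims "will establish the safety and efficacy of combination therapy with carfilzomib/PLEx/IVIG for AMR after lung transplantation". Section 4.4.3 also says that a 1:1 retrospective control group, treated with the historic standard of care, will be used to describe differences in these outcomes.

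**The concern.** The safety claim is for a combination, but the two gravest safety outcomes are conditional on one component being blamed. The trial is open-label with a single arm, so the judgement is unblinded and has no concurrent comparator. Every patient receives carfilzomib together with PLEX, IVIG, central lines and premedication, close together in time. If an investigator ascribes a kidney failure or a death to one of the other components, neither named outcome registers it, although the regimen under study produced it.

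At stake are the headline organ-failure and death figures. They would be read as the safety result of the regimen, and they are meant to be set beside a control group.

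**Working it through.** **Plan's own figure.** Section 5.13.3 sets the sample size from expected enrolment: 10 patients per year x 3 years = 30. This reproduces. The plan gives no expected rate for either outcome, so the rest of the check traces the definitions.

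**Overlap of components (Appendix A).**

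- PLEX: days 1, 3, 5, 7, 9, 11, 13, 15 (8 sessions), each followed by IVIG.
- Carfilzomib: days 1, 2, 8, 9, 15, 16 (6 doses).
- Same day: 1, 9 and 15, which is 3 of 6 doses. On those days section 5.3 places carfilzomib between PLEX and IVIG.
- Other doses: days 2, 8 and 16 each fall one day from a PLEX session.

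No carfilzomib dose is more than one day from PLEX and IVIG, so timing gives little help in separating causes.

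**Where an event is counted, by the cause the investigator gives.**

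| Event and ascribed cause | 4.4.3.1 | 4.4.3.7 | 4.4.2.4 | Still visible in |
|---|---|---|---|---|
| Organ failure, carfilzomib | yes | – | – | 4.4.3.3, AE/SAE summaries |
| Organ failure, wholly PLEX, IVIG or other component | no | – | – | 4.4.3.3, AE/SAE summaries |
| Death, carfilzomib | – | yes | no | SAE summaries, mortality curve |
| Death, AMR | – | no | yes | SAE summaries, mortality curve |
| Death, wholly PLEX, IVIG or other component | – | no | no | SAE summaries, mortality curve |

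The last row is the gap for deaths: no named death outcome holds such an event.

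**Control group.** A control treated with historic standard of care, and so without carfilzomib, cannot have an event attributable to carfilzomib. Outcomes 4.4.3.1 and 4.4.3.7 are therefore 0 in the controls whatever happened to them. Any difference described is simply the carfilzomib-arm count.

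**Scale at n = 30 (exact Clopper-Pearson 95% intervals).**

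- One event counted: 1/30 = 3.3%, interval 0.1% to 17.2%.
- The same event reattributed: 0/30 = 0%, upper limit 1 - 0.025^(1/30) = 11.6%.

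Each reattributed event moves its outcome by 1/30 = 3.3 percentage points.

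**How often this could arise.** The documents give no risk of organ failure or death ascribed to the other components, so a range is assumed. The chance of at least one such event in 30 patients is 1 - (1 - p)^30:

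- p = 1%: 26%
- p = 3%: 60%
- p = 5%: 79%

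**The case against.** The strongest reply is that little is hidden. Section 6.1.2 defines AEs whatever their attribution. Outcome 4.4.3.3 counts any AE, including grade 5. Section 6.3.4 makes every death an SAE, section 5.13.2 summarizes SAEs separately, section 5.13 plots mortality, and section 4.5 has the DSMB review any SAE. A culture-proven line infection counts under 4.4.3.5. All of this stands up to the day-90 window. It means the data for a better count already exist. It does not repair the two named outcomes, because section 5.13.2 summarizes AEs by event, system and grade, and no analysis is planned for all-cause organ failure.

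A second reply is that the stated design concerns adding carfilzomib to conventional therapy, and that PLEX and IVIG are listed as standard of care in Appendix A. Attribution to the investigational drug is therefore a legitimate question. That also stands, and it is why the carfilzomib-attributed count should be kept. But section 5.3 places PLEX and IVIG under study treatment, and the claim in section 3.1 covers the combination.

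A reader might also infer that section 6.2.3 contradicts the rules that refer to protocol-mandated interventions. It does not. Before the first dose, "only SAEs due to protocol mandated interventions will be recorded" is a recording rule with its own built-in judgement, and section 6.2.3 applies only to events already recorded. The items "Complications that occur as a result of protocol-mandated interventions" and "AEs that occur prior to the assignment of study treatment that are related to a protocol-mandated intervention" are examples listed under a definition that holds whatever the attribution.

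**Conclusion.** The point holds for outcomes 4.4.3.1 and 4.4.3.7, and for deaths that fall between 4.4.3.7 and 4.4.2.4. As worded, these outcomes can miss serious harm from the regimen, they rest on an unblinded judgement that the design supports poorly, and they are uninformative against the controls. One reattributed event is the difference between 3.3% and 0%, with the upper limit falling from 17.2% to 11.6%. This assumes 30 evaluable patients (section 5.9 allows replacements, so the denominator may be larger) and controls who received no carfilzomib.

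Three stronger readings are not supported:

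- That the error always favours the regimen. A carfilzomib-only count cannot exceed the count for any component. But an investigator may also blame carfilzomib for an event due to AMR or background illness, which errs the other way.
- That events with several causes are excluded. No section says so. Section 6.3.4 speaks of contributing factors, and section 6.3 processes a death of unknown cause as a SUSAR.
- That the 4.5% for acute kidney injury of grade 3 or above in section 6.1.4 sizes the problem. That figure is not for irreversible failure, and it comes from a table of AEs related to carfilzomib, so it says nothing about harm from PLEX or IVIG.

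**What to change.** - In 4.4.3.1, 4.4.3.7 and the synopsis, make the all-cause counts of irreversible non-lung organ failure and of death, from day 1 to day 90, the safety result for the regimen. Use these counts for any description against the controls.
- Report the carfilzomib-attributed counts beside them as a descriptive subset.
- State the day-90 limit in both places. The synopsis already ends the death outcome at day 90, while 4.4.3.7 has no end. After the day-90 window, section 6.2.1 records only SAEs related to study drug, so an all-cause count is not supported beyond it.
- In 6.2.3, add one item: relatedness to the study regimen as a whole (carfilzomib, PLEX, IVIG, lines, premedication). Attribution to each component is not needed, and the design could not support it.

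The cost is wording in the protocol and one added AE item, with no extra visits, samples or patients. The AE form is not among the documents, so its present fields are unknown. The controls' records must be abstracted for the same all-cause events over a matching window. The downside is that the reported counts may be slightly less favourable and will include events due to underlying disease, which the attributed subset helps the reader to judge.
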